13.6 Gender and Minorities

Projected Minority Inclusion

Ethnic Category	Gender		
	Females	Males	Total
Hispanic or Latino	NA	14	14
Not Hispanic or Latino	NA	83	83
Ethnic Category: Total of all subjects*	NA	97	97
Gender			
Racial Category	Females	Males	Total
American Indian or Alaskan Native	NA	2	2
Asian	NA	6	6
Black or African American	NA	16	16
Native Hawaiian or other Pacific Islander	NA	2	2

Ethnic Category	Gender		
	Females	Males	Total
White	NA	57	57
Racial Category: Total of all subjects*	NA	97	97

NA = Not Applicable

14.0 DATA SAFETY MONITORING PLAN

14.1 Data Safety Monitoring Committee and Institutional IRB reporting

A data safety monitoring committee including radiation oncologists not participating in this trial will be formed to review toxicity endpoints and efficacy data. In the phase I component, the data safety monitoring committee will review and verify all reported DLTs. In particular, this committee will scrutinize the grading of adverse events and the attribution to therapy previously assigned by the investigators. This panel will have access to basic patient information so as to have the ability to critically review toxicity events. This study will use this committee to perform ongoing safety assessment at regular defined intervals defined in the statistics section of this protocol. Unexpected toxicities occurring between defined interim analyses points will be reported to the treating center's IRB and also to the University of Texas Southwestern IRB.

14.2 Early Stopping for Toxicity

In phase I, stopping for toxicity will be related to dose limiting toxicity as described in the statistical section. Early stopping of the phase II portion of this protocol will be based on unacceptable toxicity, defined as grade 3 - 5 toxicity related to the following organ systems: gastrointestinal, renal, genitor-urinary, sexual, reproductive, neurological, blood, bone marrow, or constitutional symptoms OR any other grade 4 or 5 toxicity attributed to the therapy occurring in 30% or more of treated patients. If a single patient has more than one unacceptable toxicity, they will only be counted as one unacceptable toxicity for this analysis.

Three interim analyses of toxicity are planned after 25% (12 patients), 50% (24 patients), and 75% (36 patients) of the total number of evaluable patients to be accrued in phase II. These interim analyses will be done after patients have finished their toxicity assessment periods for each group (i.e., 90 days of post therapy follow-up).

The following early stopping rules reject the null hypothesis that the toxicity rate is less than or equal to 10% in favor of the alternative hypothesis that the toxicity rate is at least 30% with an overall Type I error rate of no more than 0.05⁵:

- 6 or more cases of unacceptable toxicities out of the first 12 evaluable patients, or
- 7 or more cases of unacceptable toxicities out of the first 24 evaluable patients, or
- 8 or more cases of unacceptable toxicities out of the first 36 evaluable patients.

The final analysis will test the same null hypothesis using the rejection rule of 10 or more patients with unacceptable toxicities out of the total sample of 47 evaluable patients. This will insure an overall significance level of 0.05 for the final conclusion. If more than 47 of the 50 accrued patients are evaluable, then the first 47 evaluable patients will be used for this analysis.

If the number of unacceptable toxicities observed demonstrate via the monitoring rules above that the treatment-related unacceptable toxicity rate is 30% or more, consideration

will be initiated for stopping the study. In this case, the study chair, study PIs, and statistician will review the toxicity data along with the Data Safety Monitoring Committee and make appropriate recommendations about continuing the study. Additionally, the treatment-related unacceptable toxicity rate will continue to be monitored during the five year follow-up period. If the unacceptable toxicity rate exceeds 30% at any time during the five year follow-up period, the study chair, study PIs, and statistician will review the toxicity data along with the Data Safety Monitoring Committee and make appropriate recommendations about reporting the information.

14.3 Reporting Requirements and Responsibilities of the Organizing PI to the USAMRMC, ORP, and HRPO:

The protocol will be conducted in accordance with the protocol submitted to and approved by the USAMRMC ORP HRPO and will not be initiated until written notification of approval of the research project is issued by the USAMRMC ORP HRPO.

Accurate and complete study records will be maintained and made available to representatives of the U.S. Army Medical Research and Materiel Command as a part of their responsibility to protect human subjects in research. Research records will be stored in a confidential manner so as to protect the confidentiality of subject information.

All unanticipated problems involving risk to subjects or others, serious adverse events related to participation in the study and subject deaths related to participation in the study should be promptly reported by [contact]), by email ([contact]), or by [contact]) to the USAMRMC, Office of Research Protections, Human Research Protection Office. A complete written report will follow the initial notification. In addition to the methods above, the complete report will be sent to the U.S. Army Medical Research and Materiel Command, ATTN: MCMR-ZB-PH, [name].

Any deviation to the protocol that may have an effect on the safety or rights of the subject or the integrity of the study must be reported to the USAMRMC ORP HRPO as soon as the deviation is identified.

Major modifications to the research protocol and any modifications that could potentially increase risk to subjects must be submitted to the USAMRMC ORP HRPO for approval prior to implementation. All other amendments will be submitted with the continuing review report to the USAMRMC ORP HRPO for acceptance.

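### Section 14.2 reads the phase II toxicity boundaries only after each full group completes 90 days of follow-up, so a count already at its limit is not formally acted on for months

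*Combined protocol and SAP*

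**What the plan says.** Section 14.2 gives the phase II rules for early stopping. They "reject the null hypothesis that the toxicity rate is less than or equal to 10"%; the opposing hypothesis is a rate of 30% or more, and the error of wrongly crossing is capped at 0.05 overall. The interim boundaries are:

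- look 1: "6 or more cases of unacceptable toxicities out of the first 12 evaluable patients"
- look 2: "7 or more cases of unacceptable toxicities out of the first 24 evaluable patients"
- look 3: "8 or more cases of unacceptable toxicities out of the first 36 evaluable patients"

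The final rule is "10 or more patients with unacceptable toxicities out of the total sample of 47 evaluable patients".

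Timing is set by one sentence: "These interim analyses will be done after patients have finished their toxicity assessment periods for each group". The period is 90 days of follow-up after therapy. When a boundary is crossed, consideration "will be initiated for stopping the study", through a review by the study chair, investigators and statistician with the Data Safety Monitoring Committee. Section 14.2 does not say whether enrolment continues while a group matures or while that review runs. Phase I is different: section 13.1.3 assesses patients as they reach 90 days, and suspends enrolment if 15 are enrolled before follow-up is adequate.

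**The concern.** Each boundary is a count within a fixed set of patients. Once the 7th confirmed case has occurred among the first 24 patients, nothing that happens to the others can undo the crossing. As written, the count is still not read until patient 24 has been enrolled, treated and followed for 90 days.

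At stake are the patients who start treatment between the moment the criterion is met and the moment it is read. The wait protects nothing statistically, because acting earlier on the same boundaries rejects on the same outcomes.

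**Working it through.** **1. The plan's own error rate.** Let r = 6, 7, 8, 10 be the boundaries at n = 12, 24, 36, 47. Let f_j(k) be the probability of reaching look j uncrossed with cumulative count k:

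- f_1(k) = Bin(k; 12, p)
- f_j(k) = sum over i < r_(j-1) of f_(j-1)(i) × Bin(k − i; n_j − n_(j-1), p)
- P(cross at look j) = sum over k ≥ r_j of f_j(k)

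| True rate | 6/12 | 7/24 | 8/36 | 10/47 | Total |
|---|---|---|---|---|---|
| 10% | 0.0005 | 0.0071 | 0.0176 | 0.0054 | 0.0306 |
| 30% | 0.118 | 0.495 | 0.278 | 0.056 | 0.946 |

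The stated limit of 0.05 is respected. At 30%, 0.890 of the 0.946 falls at interim looks. Looks 2 and 3 carry 0.772/0.890 = 87% of that.

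**2. The same boundaries applied when the count is reached.** Confirmed counts do not fall, so the event that the count reaches r within the first n patients is identical to the event that the completed group holds at least r cases. A patient-by-patient recursion gives the same totals: 0.0306 at 10% and 0.946 at 30%.

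**3. A single illustration.** Section 13.3.2 gives accrual over three to four years. With 50 patients that is 50/48 = 1.04 to 50/36 = 1.39 per month. Assume a 12-day course; with 90 days of follow-up that is 102/30.4 = 3.36 months. Suppose the 7th case is confirmed when patient 22 has just been enrolled.

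- Time to the look: 2/1.39 + 3.36 = 4.8 months, to 2/1.04 + 3.36 = 5.3 months.
- Further patients enrolled: 2 + 3.36 × 1.04 = 5.5, to 2 + 3.36 × 1.39 = 6.7.

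**4. Average size.** Simulation of 20,000 trials per setting at a true rate of 30%, with Poisson accrual at those rates, every patient evaluable and no enrolment hold. Excess means patients enrolled between the first time any boundary count is reached and the look that reads it. Ranges cover 36- and 48-month accrual.

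| Assumed onset | Mean delay (months) | Mean excess patients |
|---|---|---|
| All on the last day of the window | 3.0–3.9 | 4.1 |
| Uniform over the window | 4.5–5.6 | 5.8–6.3 |
| All in the first 1.5 months | 5.5–6.5 | 6.9–7.7 |

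With uniform onset, the 10th to 90th percentile of the excess is 1 to 11–12 patients. By look, the mean excess is 3.0–3.5 (look 1), 5.8–6.4 (look 2) and 6.8–7.3 (look 3). With onset at the end of the window, the median delay at look 1 is only 0.5–0.7 month.

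**5. Overlap with phase I.** Section 13.3.2 counts phase I patients at the phase II dose within the 50. Section 13.1.2 treats the MTD as exceeded at 3 of 9, 4 of 12 or 5 of 15. Assume these patients are the first evaluable ones and that a DLT approximates an unacceptable toxicity. Then 6 of 12 cannot arise: 0 of 7 plus 5 gives at most 5, and 2 of 9 plus 3 gives at most 5. Repeating step 4 on trials that pass this rule, interim crossing falls from about 0.89 to about 0.80 (rule applied at 9 patients) or about 0.76 (applied through 15). The mean excess is then 3.7 (late onset) to 6.2 (uniform onset).

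**The case against.** Scheduled looks at completed groups are a normal design, and no error in the plan has been shown. That stands: this is an improvement, not a correction of the error rate.

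A reader might infer that toxicities go unnoticed between looks. The documents do not support that. Sub-sites report grade 3–5 events within 48 hours (6.10.1), the medical monitor reviews serious adverse events (10.5.7), six-monthly reports include toxicity frequencies (13.5), and the committee makes ongoing assessments (14.1). If someone noticed the count at the next six-monthly report, the mean delay would shrink to about 2.5 months and 2.5–3.2 patients. These channels soften the problem without closing it, because none is told to apply the boundary. The 30% check in 14.2 that operates at any time belongs to the five-year follow-up and leads to recommendations on reporting.

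A reader might also infer that patients are treated after the protocol has judged the regimen too toxic. A crossing only opens a review, and 14.1 has the committee scrutinise grading and attribution, so a merely reported count is not final.

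Extreme runs of cases in the very first patients are tempting illustrations of a long wait. If phase I patients come first, section 13.1.2 would already have acted on most of them. The two definitions do differ: 14.2 also counts grade 3 constitutional and blood or marrow events, and its window runs from the end of therapy. So look 1 crossings are unlikely rather than excluded. Larger figures from faster accrual lie outside the rate in 13.3.2.

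Finally, silence about a hold in 14.2 does not prove that enrolment would continue.

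**Conclusion.** The point holds as a cheap improvement. Followed literally, 14.2 leaves a boundary that is already certain without formal action until the whole group has matured. At a true 30% rate and accrual over 36–48 months, about 4–6 further patients on average start treatment over roughly 3–6 months. Late to uniform onset gives that range, and consistently early onset would give about 7–8 patients. If screened phase I patients come first, interim crossing is about 0.75–0.80 instead of 0.89, and the mean excess remains about 4–6 patients given a crossing. The practical weight lies on looks 2 and 3.

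The gap in the wording is firm. Its size rests on assumed accrual, onset timing, course length, evaluability and no pause in enrolment.

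**What to change.** Replace the timing sentence in 14.2 with:

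> A boundary is met as soon as the 6th, 7th or 8th patient with a confirmed (graded and attributed) unacceptable toxicity within the assessment period is counted among the first 12, 24 or 36 evaluable patients respectively, whether or not the rest of the group has been enrolled or followed. The review with the Data Safety Monitoring Committee then starts at once, and new enrolment is paused until it has made its recommendation.

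Keep the completed-group looks for declaring that a boundary was not met. The word confirmed is essential: if reported events could trigger the rule and later be downgraded, the equivalence in step 2 would fail.

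The cost is a running tally, prompt confirmation of cases, and a short enrolment pause when a boundary is reached. Boundaries, sample size, type I error and power stay as they are.

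### The final toxicity boundary in section 14.2 (10 of 47) keeps the promised 0.05 ceiling but is one event higher than that level requires: the attained overall error is 0.031, and 9 of 47 would give 0.047 with better detection.

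*Combined protocol and SAP*

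**What the plan says.** Section 14.2 (Early Stopping for Toxicity) tests the "null hypothesis that the toxicity rate is less than or equal to 10" per cent against the "alternative hypothesis that the toxicity rate is at least 30" per cent, with the overall type I error stated as a ceiling of 0.05. The three interim boundaries are "6 or more cases of unacceptable toxicities out of the first 12 evaluable patients", "7 or more cases of unacceptable toxicities out of the first 24 evaluable patients" and "8 or more cases of unacceptable toxicities out of the first 36 evaluable patients". The final analysis tests the same null hypothesis "using the rejection rule of 10 or more patients with unacceptable toxicities out of the total sample of 47 evaluable patients". Of that final rule the section says: "This will insure an overall significance level of 0.05 for the final conclusion". The denominator is fixed. If more than 47 of the 50 accrued patients are evaluable, "then the first 47 evaluable patients will be used for this analysis". Crossing a boundary leads to review by the study team and the Data Safety Monitoring Committee, not to an automatic stop. The section gives no power for this rule and no formula for the boundaries.

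**The concern.** The section describes the error level in two ways: first as an upper limit, then as the level that the final rule delivers. If the second is read as the attained size, it should be close to 0.05 as far as a discrete rule allows.

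This is a safety test, in which rejecting the null hypothesis means declaring toxicity excessive. Permitted error that goes unused is detection given up, so the final conclusion is more lenient to the treatment than the stated level requires. Because no power is printed, the reader cannot see how much is given up.

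**Working it through.** **Inputs, all from section 14.2.** Null rate 0.10; alternative 0.30; looks at n = 12, 24, 36 and 47, so increments m of 12, 12, 12 and 11; rejection at r = 6, 7, 8 and 10 or more events; overall error ceiling 0.05.

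**Method.** Let f_k(s) be the probability of s events at look k with no earlier boundary reached. Then f_k(s) = Σ_j f_{k−1}(j) × Bin(s − j; m_k, p), summed over j < r_{k−1}. The probability of first rejecting at look k is the sum of f_k(s) over s ≥ r_k, and the overall probability is the sum over the four looks. Patients are taken as independent with a common rate p.

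**The plan's own figure, p = 0.10.** With 10 of 47:

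0.00054 + 0.00705 + 0.01764 + 0.00536 = 0.0306.

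The ceiling of 0.05 is met. The unused part is 0.05 − 0.0306 = 0.0194, or 0.0194/0.05 = 39% of the allowance.

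**Other final boundaries, interim looks unchanged, p = 0.10.**
- 9 of 47: 0.00054 + 0.00705 + 0.01764 + 0.02207 = 0.0473.
- 8 of 47: 0.00054 + 0.00705 + 0.01764 + 0.06809 = 0.0933.

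So 9 is the smallest final boundary that stays within 0.05.

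**Probability of crossing any boundary.**

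| True rate | Final 10 of 47 | Final 9 of 47 | Difference |
|---|---|---|---|
| 10% | 0.031 | 0.047 | 0.017 |
| 15% | 0.210 | 0.283 | 0.073 |
| 20% | 0.534 | 0.631 | 0.097 |
| 25% | 0.810 | 0.872 | 0.062 |
| 30% | 0.946 | 0.970 | 0.023 |

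Differences are taken before rounding. Each is the probability of ending with exactly 9 of 47 (19%) without having crossed an interim boundary, which is the only outcome on which the two rules disagree.

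**Sensitivity to how the final conclusion is read.** If it rested on the last look alone, ignoring interim crossings, the error would be 0.016 with 10 and 0.041 with 9. Nine stays within 0.05 on that reading too.

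**Sensitivity to the denominator.** With 50 patients at the last look, 9 would give 0.0625 and 10 would give 0.0365, so 10 would be needed. With 48, 9 would give 0.0519. The section fixes the analysis at the first 47 evaluable patients, so the extra accrued patients do not explain the choice of 10.

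**The case against.** The strongest reply is that nothing promised is broken. The governing statement is a ceiling, and 0.031 is under it. The later sentence naturally refers to the nominal level, and a discrete rule seldom attains its nominal level; 9 of 47 does not attain exactly 0.05 either. Spending less than the permitted error is a legitimate choice. This stands, and it rules out describing the point as a failure of type I error control. It does not account for the whole gap, because the next boundary down reaches 0.047 without exceeding the limit.

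A reader might also infer that 10 is a slip for 9. A normal-approximation boundary, x = 0.10n + 1.645 × √(47 × 0.10 × 0.90), gives x = 4.583, 5.783, 6.983 and 8.083 at the four looks. Rounding to the nearest integer and adding 1 gives 6, 7, 8 and 9. But rounding up and adding 1 gives 6, 7, 8 and 10, which are all four printed boundaries. The interim looks cannot separate the two conventions. Section 14.2 prints neither a formula nor a rounding rule, and the listing of a paper on one-sample multiple testing among the references does not supply one. The documents therefore do not show that 10 breaks a pattern.

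Nor is any stated power contradicted. The 90% power and the 23% unacceptable rate in section 13.3.2 belong to the late GU/GI hazard test, which has a different endpoint and a different alternative.

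Finally, the practical effect is limited. The interim looks are unaffected, accrual is essentially complete by the final look, a crossing prompts review only, and toxicity monitoring continues through the five-year follow-up. This bears on the size of the point and does not remove it.

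**Conclusion.** The point holds as a modest improvement in efficiency and reporting. The printed rule controls the error as promised, with attained overall error 0.031, and its final boundary is one event higher than a 0.05 level requires. The cost in detection is 2.3 percentage points at the 30% alternative and about 6 to 10 points at true rates of 20% to 25%. The wording about a 0.05 significance level is accurate only as a nominal level. These figures assume independent patients with a common toxicity rate, the boundaries as printed, a crossing at any look counted as rejection, and exactly 47 patients at the final look.

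**What to change.** Preferred: in section 14.2, set the final statistical boundary at 9 or more of 47, leave the interim boundaries as they are, and report the exact overall error (0.047) and power (0.970 at 30%). The cost is one number in the protocol and a rise in the false-rejection probability from 0.031 to 0.047, still within the plan's limit. At a true rate of 15%, only moderately above the null, the probability of declaring excess also rises, from 0.210 to 0.283. The change depends on keeping the analysis at 47 patients.

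Alternative: if 10 was chosen deliberately as a conservative boundary, keep it, say so, and replace the sentence claiming a 0.05 level with the attained error of 0.031 and power of 0.946 at 30%. This costs one sentence and leaves the test unchanged.

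In either case, state how the boundaries were derived, including the rounding rule. Sample size and the timing of the looks are unaffected.

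### The final phase II toxicity test is capped at the first 47 evaluable patients, which sets aside up to three men with complete data although the stated 0.05 error limit does not require it.

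*Combined protocol and SAP*

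**What the plan says.** Section 14.2 (Early Stopping for Toxicity) describes the unacceptable level of phase II toxicity as "occurring in 30% or more of treated patients". The test itself is counted in evaluable patients. The null hypothesis is a rate of 10% or less, the alternative is 30% or more, and the overall type I error is to be at most 0.05. The interim boundaries begin with "6 or more cases of unacceptable toxicities out of the first 12 evaluable patients", followed by 7 of 24 and 8 of 36. The final boundary is 10 of 47.

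For any surplus the section says: "If more than 47 of the 50 accrued patients are evaluable, then the first 47 evaluable patients will be used for this analysis".

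On timing it says: "These interim analyses will be done after patients have finished their toxicity assessment periods for each group", and gives the period as 90 days after therapy. Neither 14.2 nor any other section defines evaluable. The nearest text is in 13.3.2, where 47 is raised to 50 to allow for 5% of cases being ineligible or lacking data.

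The last paragraph of 14.2 keeps the unacceptable-toxicity rate under review for five years, triggered above 30%, and states no cap on the number of men.

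**The concern.** The 50 is 47 plus an allowance for loss. If the loss does not occur, the plan does not use the spare men. It sets aside one, two or three of them at the final toxicity test, although they were treated and their data are complete.

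At stake is the final conclusion on unacceptable toxicity. Nine events in the first 47 (19.1%) does not reject. If all three remaining men also had events, the total would be 12 of 50 (24.0%), a higher proportion than the 10 of 47 (21.3%) that does reject. That is the extreme case, but a tenth event in man 48, 49 or 50 would be enough to make the capped and uncapped conclusions differ.

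The shift from treated patients in the description to evaluable patients in the boundaries adds an ambiguity. A reader cannot tell how a man is counted if he has an unacceptable toxicity and then leaves follow-up before 90 days.

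**Working it through.** **Inputs, all from 14.2:** null rate 10%, alternative 30%, overall type I error at most 0.05; boundaries 6/12, 7/24, 8/36, 10/47; 50 accrued. At most 50 − 47 = 3 men are set aside.

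**Method.** Exact binomial recursion. Start with no events. At each look, add the events among the new men, binomial with probability p. Record the probability of being at or above the boundary, remove those paths, and carry on. The overall rejection probability is the sum over the four looks.

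**The plan's own figure.** At p = 0.10 with a final rule of 10/47:

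0.0005 + 0.0071 + 0.0176 + 0.0054 = 0.0306.

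The stated limit of 0.05 is met. Power at 30% is 0.946.

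**Without the cap.** Same interims, final rule 10 or more of n:

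| n | Type I error at 10% | Power at 20% | Power at 30% |
|---|---|---|---|
| 47 | 0.0306 | 0.534 | 0.946 |
| 48 | 0.0323 | 0.553 | 0.953 |
| 49 | 0.0342 | 0.573 | 0.960 |
| 50 | 0.0365 | 0.594 | 0.965 |

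The boundary of 10 therefore stays under 0.05 for every possible n from 47 to 50. For 50 men, 9 would be too low (0.0625), and 11 would be unnecessarily strict (0.0279, power 0.944 at 30%).

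**Chance that three extra men change the conclusion.** This requires no rejection at any look up to 47 men, then enough events in the last three to reach 10. Let P(k) be the probability of reaching man 47 with k events and no boundary crossed. The chance is

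P(9)·Pr(≥1 of 3) + P(8)·Pr(≥2 of 3) + P(7)·Pr(3 of 3).

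- p = 0.10: 0.0167 × 0.271 + 0.0460 × 0.028 + 0.0924 × 0.001 = 0.006
- p = 0.20: 0.0974 × 0.488 + 0.1192 × 0.104 + 0.1064 × 0.008 = 0.061
- p = 0.30: 0.0234 × 0.657 + 0.0167 × 0.216 + 0.0087 × 0.027 = 0.019

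These equal the differences between the n = 50 and n = 47 rows above, as they should.

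**Check on how early events are counted.** Suppose men still in follow-up at an interim were counted only once they had an event. The event count would then be inflated against the fixed denominators of 12, 24 and 36. A simulation at a 10% rate, assuming four such men at each interim and a final rule of 10/50, gives a type I error of about 0.043 if half their events have already occurred and about 0.051 if all have. The second figure breaks the limit, so the wording of the repair matters.

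**The case against.** The strongest defence is that the cap is prespecified, matches the number for which the boundary was set, and selects by order rather than outcome. It affects three men at most, and at the design alternative of 30% it costs about two points of power. All of that stands, and it is why this is a cheap improvement and not a serious flaw. What does not stand is any need for the cap to protect the 0.05.

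Three stronger readings are tempting and are not supported.

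- *Men who leave before 90 days are excluded.* The 90 days is given only for the timing of the interims. Evaluable is undefined, and a man with a recorded severe toxicity is not obviously a case lacking data under 13.3.2. The documents show an ambiguity, not an exclusion. Excluding men who left because of toxicity would bias the rate downward, but no section says that this is done.
- *The last men drop out of safety oversight.* The cap applies to the final test only. Event reporting (6.10), the six-monthly reports (13.5), the monitoring committee (14.1) and the five-year review in 14.2 carry no such limit. The late-toxicity analysis in 13.5.2 has no cap either. The five-year review does not replace the lost test, however: its trigger is above 30%, so 12 of 50 (24.0%) would not reach it.
- *The effect is large because the three men will often include an event.* That chance is 1 − (1 − p)³, or 27%, 49% and 66% at rates of 10%, 20% and 30%. It is not the chance that the conclusion changes, which is 0.6%, 6.1% and 1.9%.

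**Conclusion.** The point holds in a limited form. Section 14.2 leaves up to three men with complete data out of the final toxicity test, and the stated error limit does not require it. Using all 50 raises type I error from 0.031 to 0.037 and power from 0.946 to 0.965 at a 30% rate, or from 0.534 to 0.594 at 20%, a rate that is not a design point of this rule. The plan's statement that overall error is at most 0.05 is correct as written.

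The figures assume independent patients with one common toxicity probability, looks at exactly 12, 24 and 36 men, and a binding boundary. In the plan, crossing a boundary prompts a review, not an automatic stop. The view that the cap loses information without bias assumes that toxicity does not drift with order of enrolment. If some event-free men leave early and are passed over, the counted group would contain slightly more events than assumed here. The documents give no basis for sizing that.

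**What to change.** 1. Delete the sentence that limits the final test to the first 47. State instead that the final analysis uses all evaluable phase II patients (47 to 50) and rejects at 10 or more with unacceptable toxicity.
2. Report the exact overall type I error for the realised number: 0.031 at 47, 0.032 at 48, 0.034 at 49, 0.037 at 50.
3. As a clarification, define evaluable so that a treated man with an unacceptable toxicity before 90 days counts, in his place by order of enrolment.
4. Keep the interim denominators at the first 12, 24 and 36 by order of enrolment. Each look waits until every one of those men has completed 90 days or had an event, so that men still in follow-up do not enter only through their events.

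The cost is a few sentences in 14.2, with no new patients or data. The downside is the rise in type I error from 0.031 to at most 0.037, within the stated 0.05. The change does not turn the test into one on all treated men, because event-free men who leave early could still fall outside it. It also supplies no final boundary for fewer than 47 evaluable men, which the plan does not give either.
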